13. ALTERNATIVES TO PARTICIPATION

The alternative to participation is non-participation.

14. POTENTIAL RISKS

Potential risks for study participation in the focus groups and survey include loss of confidentiality as a result of participating in this study. It is possible that participants may disclose confidential information about themselves. In order to provide participants with as much opportunity as possible to control access to information about themselves, recruitment and consent procedures will include thorough explanation of the purpose of the study, what participation entails, risks and benefits of participating in the study. Participants will also be told explicitly that participation is voluntary, consent can be withdrawn at any time during the study, and that there are no consequences for withdrawing from the study. Furthermore, a policies and procedures manual for the project will specify immediate data monitoring and response. Participants will be informed during the consent procedure that confidentiality may be breached under certain circumstances (i.e. they are a danger to themselves or others). In cases where a breach of confidentiality is necessary, project staff will be instructed to report to the project coordinator, who will file an incident report with [name] within 24 hours. The incident report requires a detailed account of the problem, date of occurrence, date it came to the PI's attention, impact on participant and corrective action taken. [name] will report adverse events to the UCSD IRB to make a determination if the event was related to research, directly or indirectly, and, if so, require revisions of protocol or consent, as applicable, and re-review of these procedures by the IRB with copies to the Office of Human Subjects for any necessary further action. Project staff hired through UCSD will be required to obtain ethical training through the CITI program (i.e., Social-Behavioral course) so that they are aware of the responsible conduct of research, and the types of adverse events that may warrant a breach of confidentiality. Monitoring of potential adverse effects or serious problems will be given high priority by project staff and researchers. All project staff will receive verbal and written instructions pertaining to the rules governing the maintenance of confidentiality upon completion of the study or if they leave the study before its completion. As previously mentioned, we are using an existing program to schedule participants follow-up appointments for the 2nd dose (NextGen) is currently being utilized by SYH because it is a safe and secure resource. NextGen sends automated reminders masking the direct line's outgoing and incoming phone numbers for text messaging and email reminders. Although there is no link between identity and the data (i.e., the unique code linking the surveys does not link to identifying information) this research is protected by the NIH Certificate of Confidentiality (CoC). The CoC will protect the privacy of research subjects by prohibiting disclosure of identifiable, sensitive research information to anyone not connected to the research.

Many people can experience a slight nervousness or discomfort at the prospect of being interviewed or expressing their opinions in a group discussion. The focus group questions asked to the participants may be embarrassing and upsetting, as they reflect upon their thoughts about COVID-19 and the vaccine. Asking about their behaviors or beliefs could be a sensitive matter. RAs will stress to everyone who chooses to participate that they should feel free to decline to answer any question they wish and may terminate the FG or interview at any time. Seriousness, respect, and professionalism will be emphasized during the training of and supervision of the RAs. Nonetheless, it is possible that some participants may become anxious, depressed, sad, or angry due to this content, and there is a small possibility that this may result in becoming a risk to themselves or someone else. Training of RAs will include participant debriefing to detect these issues. If such issues arise, research staff will offer the participant the opportunity to speak with a trained SYH behavioral health professional. If needed, the SYH counselor will escort or refer the client to longer term behavioral health services. Our previous work in similar contexts using similar items has elicited no such responses.

Additional potential risks for study participation include a slight nervousness or discomfort at the prospect of receiving the COVID-19 vaccine (e.g., swelling or pain in the injected area) and having to complete a survey. [name] will supervise overall data collection and outreach efforts to accomplish the study objectives. SYH and [name] (Co-Investigator and licensed physician) will oversee implementation of the COVID-19 vaccine based on the U.S. Food and Drug Administration (FDA) and Centers for Disease Control and Prevention (CDC) recommendations and guidelines.^{1,23} Since enrollment will occur at participating SYH community centers and mini-vaccination stations, the researchers will follow the data safety protocols as outlined by SYH. In accordance with these guidelines, at the time of enrollment to the RCT, all patients will be assigned a unique study ID to link their responses across time. Quantitative survey data collected via tablet computers will include no personal identifiers, only the unique study ID of participants. Furthermore, registered nurses from SYH will proceed to consent for and apply the COVID-19 vaccine and will observe the participant has no reaction for 15

minutes. SYH will follow strict vaccination protocols (based on the FDA and CDC recommendations and guidelines)^{1,7} and will report all vaccine administration errors, all serious adverse events, cases of Multisystem Inflammatory Syndrome (MIS), and cases of COVID-19 that result in hospitalization or death following administration of the COVID-19 Vaccine to the IRB and to the Vaccine Adverse Event Reporting System (VAERS). Additionally, a detailed protocol has been developed by SYH to handle adverse events related to the COVID-19 vaccine, although none have occurred so far in the application of the COVID-19 vaccine. Staff members have been assigned specific responsibilities (e.g., if warranted, nurses will administer epinephrine or Benadryl and maintain an airway; outreach workers would call 911 and wait for the ambulance). The medical director of the study on behalf of SYH, [name], will be on call at all times, and a licensed nurse will manage all aspects of the COVID-19 vaccination phase. Additionally, project staff, will be responsible for immediately reporting any breaches of protocol, breakdowns in the consent process, violations of confidentiality of the data, complaints by participants or any serious problems or adverse events to the project coordinator who will file an incident report with [name]. [name] will collect any incident reports and communicate serious problems or adverse events to the UCSD HRPP, who will report to NIH if warranted.

Lastly, based on the intervention components and objectives, we do not foresee an increased risk of an individual receiving the 1st dose but not the 2nd dose as a result of participating in this project. The different *2VIDA!* individual and community research activities centered on providing health literacy and addressing vaccine hesitancy, as well as the reminders and tracking mechanisms in place (i.e., providing two additional contacts), we believe that participants from this research projects will be more likely to receive the 2nd dosage.

15. RISK MANAGEMENT

Multiple precautions will be taken to minimize the risk that research participants will become emotionally distressed and to support any participants who experience emotional distress despite these precautions. Prior to beginning the FG or interviews, participants will be reminded that some sensitive questions will be asked, that they are free not to answer any question and may terminate their participation at any point without any penalty. Our staff will be trained in accordance with the World Health Organization (WHO) guidelines for conducting research on sensitive subjects to be aware of signs that a participant is becoming distressed or fatigued due to participation in data collection. If this occurs, verbal support will be provided support and encouragement that they are free to decline such questions, such as “I know these can be difficult questions, and you can skip a question or stop the interview if you are uncomfortable for any reason.” Upon the participant’s completion of the interview or at their termination of involvement, the participant will be debriefed and screened for emotional distress: “These questions can make some people feel sad, anxious, or angry. How are you feeling now?” In addition to debriefing, all participants will be provided with service information for a variety of community resources, including mental health and social support services. No such adverse events have occurred in [name] previous projects that have employed these procedures with adults within similar contexts.

Any research involvement involves some risk of loss of confidentiality. Extensive measures will be taken to protect the confidentiality of the study participants and minimize any risk of a breach. All personal data collection will be conducted in private settings. Additionally, participants will be represented via a unique identifier for purposes of re-contact; contact/tracking information that include personal identifiers (i.e. first names, Google Voice number) will be linked with these unique identifiers on a list kept on a secured server in a password protected file, accessed only by the Research Coordinator and site Co-I at SYH. Only SYH research staff will have access to this list, and solely for identifying participants for scheduling their time for study participation. Clients unique IDs, and Google Voice number will be deleted immediately after completion of the data collection (i.e., after the 4-week follow-up). Audio-recordings from focus groups will be moved daily onto a secure UCSD server that is password-protected and backed-up daily and will be destroyed immediately after transcription is complete. Transcripts will not include personal identifiers and the document connecting personal identifying information to the list of unique survey identifiers will be destroyed as soon as data collection is completed. Additionally, research assistants and SYH clinical staff will be required to maintain confidentiality of all research participants and will be required to sign a pledge agreeing to do so upon joining the research project. They will not be permitted to report on anyone’s data or participation in this study.

All the FG participants will be asked to sign a written confidentiality agreement before participating in the session to ensure participants do not share with others outside the group what was discussed and by whom during the FG. Additionally,

during the FGs all participants will be requested to only refer to others using a pseudo name. Research assistants (RAs) will explain that confidentiality is critical to the safety and ability to share freely for all participants in the group. RAs will also remind participants that they may choose to not identify themselves or the experiences they share (for example, say that a friend had a particular experience even if it was their own experience). No identifiers will be recorded in transcripts.

Every effort will be made to minimize participants' risk of a loss of confidentiality. All research and SYH staff will be required to maintain confidentiality of all research participants and will have signed a pledge to do so upon joining the research project. If any privacy or data security arrangement is violated, either through physical tampering or breach of confidentiality, the individual making the discovery will immediately notify [name] and the SYH research team. [name] will immediately report this breach to the UCSD IRB. [name] and SYH will take immediate efforts to identify the breach, remedy it, and terminate employment of anyone directly causing it. Participants' names and other identifying information will not be used in any reports or publications.

There are some circumstances in which confidentiality will be breached by the researchers. If the participant directly informs research staff of his/her intentions of homicide or suicide, the researcher will immediately contact authorities (police or mental health) to help address the issue. However, as part of informed consent we will let all participants know this, and we do not directly assess these issues via our data collection processes. These issues have not arisen, to our knowledge, in the past across similar projects in similar contexts. Finally, if any participant reports being hurt by another person or harming another person, SYH, as mandated reporters, will contact local law enforcement. We will also inform participants of this during the informed consent process, and before data collection begins.

Data and Safety Monitoring Plan: Data and safety monitoring of study participants will focus on two major safety aspects: 1) assurance that no harm comes to participants as a result of research participation and 2) assurance that all data collection from this study maintains the privacy of research participants. Major mechanisms of precaution include the use of confidential and anonymous data. Data provided to UCSD from surveys and FGs will include no personal identifiers. Survey data and audio-recordings of FGs maintained for this study will only be labeled with unique participant identifiers; no names or other identifiers will be stored with any data collected. Only participants' first names and the Google Voice number associated with their account will be saved during the recruitment and scheduling process for the 2nd dose of the vaccine. Once the applicable data collection activity is complete, these will be immediately and permanently deleted.

All physical data collected (i.e., audio files from FGs) from this study will be transcribed and translated from Spanish to English without personal identifiers prior to electronic storage, coding, management, and analysis. Original copies of audio files that may include personal identifiers will be destroyed after transcription and/or translation are complete. Prior to translation, audio files will be secured by immediately uploading them to an encrypted server and password protected file on a UCSD computer and the audio file from the recording device will be deleted. Audio recordings of FGs will be de-identified in the process of transcription and the audio file will be deleted after it has been transcribed and verified.

All research staff collecting and translating or transcribing data from this study will sign an agreement in which they agree to maintain absolute confidentiality of all participants within this research project. All survey and FGs data analyses will occur at UCSD; electronic files will be kept on an encrypted shared project drive within UCSD's protected network. Data files on the online server and at UCSD are backed up every night to minimize the likelihood of lost files. As described above, all data with personal identifiers or that link data to personal identifiers will be destroyed as soon as it is no longer needed, i.e., after transcription or translation, or after completion of 2nd dose/follow-up survey data collection.

Additionally, to minimize any potential risks, all research staff under the direction of Drs. [name] and [name] will attend a three-day training where they are trained in supportive techniques and procedures to protect the confidentiality of participants, to ask sensitive questions without judgment, and to assess participants for signs of distress during and upon completion of the survey and receiving the vaccine. If a participant is upset or distressed at any point during data collection, the research staff are trained to offer the opportunity to speak privately with an on-site SYH counselor trained in the provision of brief mental health counseling; the counselor will refer participants to follow-up services if longer-term

assistance is needed. Lastly, a policies and procedures manual for the project will specify immediate data monitoring and response. Participants will be informed during the consent procedure that confidentiality may be breached under certain circumstances (i.e. they are a danger to themselves or others). In cases where a breach of confidentiality is necessary, project staff will be instructed to report to the project coordinator, who will file an incident report with [name] within 24 hours. The incident report requires a detailed account of the problem, date of occurrence, date it came to the PI's attention, impact on participant and corrective action taken. [name] will report adverse events to the UCSD IRB to make a determination if the event was related to research, directly or indirectly, and, if so, require revisions of protocol or consent, as applicable, and re-review of these procedures by the IRB with copies to the Office of Human Subjects for any necessary further action. Project staff hired through UCSD will be required to obtain ethical training through the CITI program (i.e. Social-Behavioral course) so that they are aware of the responsible conduct of research, and the types of adverse events that may warrant a breach of confidentiality. Monitoring of potential adverse effects or serious problems will be given high priority by project staff and researchers. All project staff will receive verbal and written instructions pertaining to the rules governing the maintenance of confidentiality upon completion of the study or if they leave the study before its completion.

16. POTENTIAL BENEFITS

The results of this study will inform local and national scale-up efforts of interventions designed to address vaccine hesitancy and increase access, acceptance, uptake and series completion of the COVID-19 vaccine among Latinx and AA adults in the U.S. Even if the intervention proves ineffective at increasing access, acceptance, uptake, and series completion of the COVID-19 vaccine among Latinx and AA communities, this information is valuable to the development of more effective models in the future and to inform efforts to ending the pandemic. Based on the study design and the nature and severity of COVID-19 infection, the potential knowledge gained from this study outweighs any potential risk and will have an impact on the health of Latinx and AA communities in San Diego that have been severely impacted by the pandemic.

17. RISK/BENEFIT ASSESSMENT

Based on previous research and efforts towards the COVID-19 vaccine development and subsequent FDA Emergency Use Authorization, we know that there is a demonstrated benefit of receiving the COVID-19 vaccine and addressing vaccine hesitancy among racial/ethnic minorities that have been severely impacted by the pandemic is critical. Health benefits are hypothesized and determining this is the purpose of the research study. Study participants will receive COVID-19 Individual Awareness & Education, COVID-19 Community Outreach & Health Promotion, COVID-19 Individual Health Education & Linkages to Medical and Supportive Services and provision of COVID-19 vaccine at participating SYH community centers and mini-vaccination stations in the communities where they live. Due to the severity of COVID-19, the high rates of infection and deaths among AA and Latinx communities and the current low uptake of the vaccine (only 14% of Latinx and 3% of AA have received at least one dose of a coronavirus vaccine compared to 60% of White individual)^{10,11} we believe that the 2VIDA! intervention is promising and the AA and Latinx communities will benefit in receiving the intervention – which centers on providing medical education and increasing access to the vaccine.

San Ysidro Health (SYH) is a non-profit Federally Qualified Health Center (FQHC) committed to providing high quality, compassionate, accessible and affordable health care services, with a mission to improve the health and well-being of the communities we serve with access for all. Originally established along the border in 1969 by seven women in search of medical services for their children, SYH is now one of the most trusted and leading providers of comprehensive safety net primary health care and support services across San Diego County. SYH primarily serves the *South Bay Region* (61% Latino), with recent expansion into 6 clinics and 1 community center in the *East County Region* (28% Latino). SYH serves a predominantly racial and ethnic minorities (85%), with high rates of poverty (69% live below the federal poverty level), uninsured individuals (21%) and families with low educational attainment and non-English speaking heads of households. As the largest community partner on this proposal, SYH will build upon existing experience with, and trust established in the local Latinx and AA communities to guide the data collection efforts of *2VIDA!* health promotion and education outreach efforts, establishment of the mini-vaccination stations and COVID-19 vaccine delivery. As a practicing licensed physician at SYH and with over thirty years of experience in public health and direct patient care, [name] (Co-Investigator) will oversee implementation of the COVID-19 vaccine based on the FDA and CDC guidelines. [name] will supervise overall data collection and outreach efforts along with [name] (PI) to accomplish the study objectives.

19. FUNDING FOR THIS PROJECT

National Institute on Minority Health and Health Disparities (NIMHD).

Cover Page for ClinicalTrials.gov

Document: Statistical Analysis Plan

Official Study Title: Project 2VIDA! COVID-19 Vaccine Intervention Delivery for Adults in Southern California

NCT number: NCT05022472

Document date: February 5, 2021

STATISTICAL DESIGN AND POWER CALCULATIONS

We will approach overall data analyses using a multivariate repeated measures design (i.e., doubly multivariate) to assess mean differences in treatment and control groups on our primary (acceptance of COVID-19 vaccine and vaccine series completion) and secondary outcome variables (increased knowledge of COVID-19 vaccine, increased access to COVID-19 vaccine, vaccine hesitancy). Additional measures at baseline and follow-up will be used as covariates (e.g., outreach and health communication, vaccine hesitancy or mistrust). Mean differences, both within and between treatment and control groups as well as group by treatment interaction effects will be analyzed. The targeted sample size is sufficient to detect a small effect size (.20) with power = .90 at alpha = .05 accounting for moderate participant attrition. Descriptive Statistics. To describe the overall sample regarding demographics, structural and individual barriers, and potential covariates of intervention effects at baseline, prevalence statistics and means and standard deviation will be provided for all baseline variables; Cronbach's alpha of .70 will be required to be considered reliable. Baseline Analyses to Detect Differences Between Treatment Groups. Chi-square analyses and paired t-tests will be used to detect differences in demographics, knowledge of COVID-19 vaccine, access to COVID-19 vaccine, acceptance of COVID-19 vaccine and series completion, COVID-19 resource-seeking behaviors and linkage into care between intervention and control groups. Demographic variables included in these analyses will be age, gender, race/ethnicity, household income, marital status, and having insurance. Those variables differing across treatment groups at the $p < .20$ level will be included in subsequent adjusted outcome analyses.

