
Mini-vaccination stations. We will set-up mini-vaccination stations in the parking of three public parks in the selected intervention sites to support the SYH community health centers. We will set-up signs with the *2VIDA!* project for participants to identify (e.g., same logo and illustrations used during Phase 1) and tent-lined lanes for eligible recipients to drive up. Research assistants will confirm eligibility with potential study participants via verbal assessment of the following inclusion criteria: 1) age 16 years or older; 2) identify as Latinx and/or AA; 3) biologically male or female; 4) be a resident of one of the three communities selected for the intervention (National City, Lincoln Park, Logan Heights, Valencia Park, San Ysidro); 5) literate in English or Spanish; 6) no known history of severe allergic reactions to any components of the vaccine; 7) no history of immune disease; 8) not be pregnant; 9) no plans to move from the area in the following 30 days; 10) able to provide voluntary informed consent; and 11) able to provide complete contact information for themselves (email and phone number) and two additional contact individuals for follow-up. Inside their car they will complete the 10-15 min. survey, receive the COVID-19 vaccine, and pull aside for a 15-minute observation period. We will also set-up additional tents with portable chairs at least 6 feet apart for participants who do not own a vehicle and want to receive the vaccine at the mini-stations. The stations will be opened Monday-Sunday from 7:00am-7:00pm based on the recommendations from our community partners (e.g., some individuals work early/late shifts). We will have two options for the vaccine – a one shot or a two-shot vaccine and the participants will select what type of vaccine they prefer. The vaccines will be available on a first come first-serve basis. For individuals who select a two-shot vaccine, the study staff will schedule the appointment for the participants on site when they receive the 1st dose of the vaccine (as they are waiting during observation period) and give them the date (confirmation). We will use the NextGen program to schedule the follow-up appointments for these participants. For participants who select a one-shot vaccine, they will be reminded that they will receive a text message and/or a link via email (based on their preference) to complete a follow-up survey in 4-weeks. Participants who select a two-shot vaccine will be asked to complete the follow-up survey (4-weeks) when they return for their second shot (during the observation period). We have noticed that percentage of our population has low digital literacy levels and/or limited access to internet or digital technologies which has made enrollment and follow-up challenging. In order to address these barriers, we are proposing to utilize Computer Assisted Telephone Interviewing (CATI)²⁰ and videoconferencing and screen sharing (VCSS).²¹ Both tools have been successfully used for many years in public health as well as by our community partner (SYH) on other similar federal-funded research projects. During enrollment, we would provide the participants with the option to complete the follow-up survey utilizing CATI or VCSS if they require assistance or have limited access to digital technologies. If they chose CATI or VCSS, following the completion of the follow-up survey we would send the incentive via a unique link similar to the follow-up for other participants. The entire team has been trained on these two platforms and would only be used for follow-up. Additionally, SYH will create a temporary patient ID for them and enter them in the system to schedule their second appointment. This is the software program that SYH is currently utilizing to follow-up for vaccine appointments. We believe that utilizing SYH existing infrastructure will allow sustainability and scalability of *2VIDA!*! The participants who select a two-shot vaccine will receive an email or automated

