10. RECRUITMENT

Six SYHealth community health centers across San Diego County have been selected based on their serving predominantly Latinx and AA client population and having the Zip codes with the highest number of COVID-19 cases in the County. These clinics are located in National City, Logan Heights, Lincoln Park, Valencia Park and San Ysidro. Each clinic will be randomly selected and randomized evenly to either the intervention or control conditions, using computer-generated randomization plans prepared using SAS statistical software under the direction of the lead study statistician. Clinic-level randomization was selected to minimize between-arm contamination of intervention and control conditions. Participants from both intervention (n=500) and control sites (n=500) will be recruited using reactive recruitment, including the use of community partner social media platforms, and flyers distributed in the SYH target health centers and high traffic, readily visible areas, where eligible participants are likely to see them (e.g., grocery stores, local CBO's, parks, barber shop, cafés, food banks, gyms, local restaurants). Flyers will include study information and contact information for study staff. Likewise, the project staff publicized the rapid vaccine effort (e.g., mini-vaccination stations) by posting flyers that noted locations, dates, and times of vaccine distribution, and through presentations about the project at community meetings. Project staffing, training, and support, including the selection of nurses and outreach staff (e.g., peer-health educators and research assistants) with complementary research skills and personal knowledge of the community will be key to the success of the project. Two bilingual Latinx (one male and one female) and two AA (one male and one female) outreach workers trained in research ethics and protocols, and familiar with this population will approach individuals who appear to be eligible (Latinx and AA adults ages 16 years or older) at the SYH community centers and mini-vaccination stations in the participating communities, confirm eligibility, and describe the study to those eligible. Research staff will update time logs and continuously update our sampling frame until recruitment is finalized. The reason for refusal or ineligibility will be recorded. Extensive efforts will be made to have an equal representation of Latinx and Black community members and at least 40% women.

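### The joint doubly multivariate model, with no missing-data method named, lets a gap in a survey scale remove a participant's primary vaccine outcomes

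*SAP*

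**What the plan says.** The SAP's statistical section begins: "We will approach overall data analyses using a multivariate repeated measures design (i.e., doubly multivariate) to assess mean differences in treatment and control groups". Protocol section 8, Data Analysis, carries the same text. The outcomes placed under this design are "primary (acceptance of COVID-19 vaccine and vaccine series completion" and "secondary outcome variables (increased knowledge of COVID-19 vaccine, increased access to COVID-19 vaccine, vaccine hesitancy", five in all. The SAP adds: "Additional measures at baseline and follow-up will be used as covariates".

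On size, the SAP states "The targeted sample size is sufficient to detect a small effect size (.20) with power = .90 at alpha = .05", "accounting for moderate participant attrition". It gives no attrition rate, effect metric or sidedness. Protocol section 10 gives the numbers: "Participants from both intervention (n=500) and control sites (n=500) will be recruited using reactive recruitment".

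On follow-up, Protocol section 8 (Mini-vaccination stations) says: "Participants who select a two-shot vaccine will be asked to complete the follow-up survey (4-weeks) when they return for their second shot". The Phase II text in the same section also places a short survey at the second-dose visit. Participants who choose the one-shot vaccine are sent a survey link by text or email at four weeks. Telephone or video completion is offered to those with limited digital access.

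Neither document states an analysis population, a complete-case rule, an imputation method or a missing-data sensitivity analysis. Vaccine uptake is listed among the items collected at baseline and four weeks (Protocol sections 5 and 8). No section names the dose record as the source of the primary outcomes.

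**The concern.** A doubly multivariate repeated-measures analysis, in its usual MANOVA form, needs every outcome at every time for each participant. With five outcomes at two waves, one missing hesitancy score removes the whole person, including whether that person was vaccinated and finished the series. Even a complete dose record would not help, because the joint model would discard it for anyone with a survey gap.

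The loss is unlikely to be random. For two-shot participants the survey is tied to the second-dose visit, so missing the dose tends to mean missing the survey. For one-shot participants the reverse can happen: the series is finished on the first day, and that completer is lost if the link is ignored. The primary comparison would then rest on a selected subset, with less precision than the enrolled sample could give and a bias whose direction is not known in advance.

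**Working it through.** **1. The plan's own power figure.** Inputs: 500 per arm (Protocol section 10), effect 0.20, alpha 0.05 (SAP). Assumed: two-sided test, standardised mean difference, individual-level analysis, no attrition.

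Power = Φ(0.20 × √(n/2) − 1.96). At n = 500: Φ(3.162 − 1.960) = 0.885, close to the stated 0.90. A full 0.90 needs 526 per arm on these terms. With 20% attrition (n = 400) power is 0.807. Clustering by the six randomised clinics is ignored because the documents give no intraclass correlation, so true power would be lower.

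**2. Share left after listwise deletion.** Suppose the vaccine outcomes are otherwise complete. Only the three survey outcomes at two waves can then have gaps: 3 × 2 = 6 cells. Let a be the share lost at follow-up and m the missing rate per cell, independent across cells. Both are assumptions.

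Share kept = (1 − a) × (1 − m)^6

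| a | m = 2% | m = 5% |
|---|---|---|
| 0% | 88.6% | 73.5% |
| 10% | 79.7% | 66.2% |
| 20% | 70.9% | 58.8% |
| 30% | 62.0% | 51.5% |

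At a = 20%: 0.80 × 0.98^6 = 0.709, or 354 per arm; 0.80 × 0.95^6 = 0.588, or 294 per arm. The formula in step 1 gives power of 0.758 and 0.679. If dose status were known for everyone and each primary outcome had its own model, n would stay at 500 and power at 0.885.

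**3. Effect of response that depends on completion.** Assumed true completion is t = 80% v 70%, with response of 95% in completers and r in non-completers, the same in both arms.

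Observed completion = 0.95t / (0.95t + r(1 − t))

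| r | t = 80% | t = 70% | Difference |
|---|---|---|---|
| 50% | 0.760/0.860 = 88.4% | 0.665/0.815 = 81.6% | 6.8 points |
| 30% | 0.760/0.820 = 92.7% | 0.665/0.755 = 88.1% | 4.6 points |
| 20% | 0.760/0.800 = 95.0% | 0.665/0.725 = 91.7% | 3.3 points |

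The odds ratio does not move. The true value is (0.80/0.20) / (0.70/0.30) = 1.71. Selection multiplies the odds in each arm by the same 0.95/r, which cancels. That holds only while response, given completion status, is equal between arms.

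**4. Direction.** Observed completion exceeds true completion only if completers respond more often than non-completers. The two-shot procedure pushes that way. One-shot participants who ignore the remote link lower the completers' response rate and push the other way. The documents give no expected split between the vaccines.

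**The case against.** Complete-case analysis is inferred from the method's name; the plan does not state it. The SAP mentions later adjusted outcome analyses without specifying them, and Aim 2 (Protocol section 5) says vaccination rates and completion will be compared between groups, which could be done outside the joint model. A likelihood-based multivariate mixed model would not delete listwise. All this stands, and a reader should not conclude that the plan restricts the analysis to complete participants. But nothing written overrides the method's default.

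A reader might count all ten outcome-by-wave cells and obtain 0.80 × 0.98^10 = 65% and 0.80 × 0.95^10 = 48%. That lets vaccine status itself have item gaps, so it does not fit the case in which vaccine outcomes are otherwise complete. Six cells is the right count there.

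The shrinking difference in step 3 comes from outcome-dependent non-response. A separate logistic model of survey-reported completion would show the same shrinkage. Independent item gaps, the part specific to the joint model, cost precision only. With equal response by arm the risk difference moves towards zero and no false effect appears. These points stand, and they are why the outcome source must change along with the model.

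A reader might also infer that completion is overstated in both arms. One-shot participants prevent that conclusion.

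Nor is vaccine status established as available without a survey. Protocol section 14 says the code linking the surveys does not lead to identities. Section 15 describes a list joining contact details to study identifiers, held at the health centre, limited to scheduling and deleted after follow-up. Linkage looks feasible but is not planned. Staff help, telephone and video follow-up, and no-show tracing will reduce the loss, by an amount the documents do not state.

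**Conclusion.** The point holds in this form: five outcomes share one doubly multivariate design, no missing-data method is named, and the design's standard form ties the primary vaccine outcomes to completeness of the survey scales. The size is illustrative. About 71% (59%) of participants remain at 20% loss and 2% (5%) missing per survey cell. If two-shot non-completers respond less, a true 10-point difference could appear as 3.3 to 6.8 points under the assumed response rates. Those rates are not in the documents, and the second result assumes equal response patterns by arm. The net direction of bias is unknown. Separating the vaccine outcomes from the survey scales is worthwhile even if listwise deletion was never intended.

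**What to change.** - Replace the joint model with one model per outcome.
- Analyse vaccine receipt and series completion as binary outcomes in all enrolled participants, by arm of the enrolling clinic, whether or not a survey was completed.
- Name the health centre's dose record as the source, with survey report as back-up. Extract it against the study identifier before the identifiers are deleted (Protocol section 15).
- Ascertain doses in the same way in both arms. Protocol section 8 describes no-show tracing as done only for 2VIDA! participants. If that means the intervention arm, counting an undocumented dose as a failure would favour the intervention. Doses given elsewhere raise a similar question.
- As sensitivity analyses, present results with no documented dose counted as not completed alongside results from multiple imputation.
- Analyse knowledge, access and hesitancy with likelihood-based mixed models that use every available observation.

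The cost is SAP wording, some extra programming and a dose-data extract. The extract may need an amendment to the confidentiality provisions in Protocol sections 14 and 15. No further participants are needed.
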